8.3.4.2. Secondary Endpoint Analyses

The secondary estimands are intended to provide a population level estimate of the treatment effect of the pamrevlumab on time-to-event endpoints and continuous endpoint, regardless of participants compliance with the IP dosing. Under estimand framework, the analysis of secondary endpoint includes the following components:

Population: Same as primary estimand.

Endpoints:

- Time to disease progression, defined as absolute FVCpp decline of $\geq 10\%$ or death, whichever occurs first
- Change in Quantitative Lung Fibrosis (QLF) volume from baseline at Week 48
- Time to any component of clinical composite endpoint, whichever occurs first: acute IPF exacerbation, respiratory hospitalization, or death
 - Time to first acute IPF exacerbation during study
 - Time to all-cause mortality during study
 - Time to first respiratory hospitalizations during study

Treatment of interest: Same as primary estimand.

Handling of intercurrent events:

For time-to-event endpoints, treatment policy strategy will be adopted. For death, composite strategy will be used if death is a component of the endpoint. Censoring rules will be defined in the SAP.

For QLF, the same strategy as primary estimand will be applied.

Population-level summary for the endpoint:

For time-to-event endpoints: The hazard ratio and corresponding 95% CI from Cox proportional hazard model will be presented. P-value from stratified Log-rank test will also be reported. Details will be defined in the SAP.

For QLF endpoint: treatment difference of Least-square mean (LSMean) and SE at week 48 between pamrevlumab and placebo and the corresponding 95% CI derived from a Mixed Model for Repeated Measure (MMRM) will be presented. The MMRM model includes treatment, visit, treatment-visit interaction, randomization stratification factor, and baseline endpoint value as fixed effects.

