8. STATISTICS

8.1. Sample Size Determination

This study will enroll approximately 340 subjects with a 1:1 randomization ratio to pamrevlumab or placebo, respectively.

A sample size of 340 subjects will have at least 90% power, based on a two-sided alpha level of 0.05 for a two-sample t-test, to detect a treatment difference of 120 mL in the primary efficacy endpoint, change from baseline in FVC (L), assuming a common standard deviation of 300 mL. This sample size allows for a dropout rate of approximately 20%.

The rationale for these sample size assumptions are as follows. In the phase 2 study FGCL-3019-067, a treatment difference of 178 mL was observed in change from baseline in FVC to Week 48. For this study, a conservative treatment difference of 120 mL is assumed. The standard deviation is estimated based on published results from other IPF studies.

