8.3.4.3. Exploratory Analyses

Patient reported outcomes (PROs) including SGRQ, UCSD-SOBQ and LCQ will be analyzed using same MMRM model as QLF. Absolute and relative FVCpp will be analyzed with similar RCM model as FVC excluding the covariates adjusted for FVCpp. Time to composite of respiratory hospitalization, absolute FVCpp decline $\geq 10\%$, or death will be analyzed similar to other secondary time-to-event endpoints. Biomarkers will be summarized.

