6.7.1.1.5. Population Summary for Treatment Comparison

Treatment difference of Least-square mean (LSMean) and SE at week 48 and the corresponding 95% CI will be presented.

All post-baseline visits for the specified parameters below during the double-blind period will be included in the analysis. Change from baseline for the specified endpoints (excluding baseline visits) will be analyzed using a Mixed Model for Repeated Measures (MMRM) approach with fixed effects for treatment, visit (as a factor), treatment-by-visit interaction, randomization stratification factor, and covariates (baseline values, sex, age, race group, and height). Example SAS code in Appendix 7.1.

The following graphical displays will be provided:

- The mean $(\pm SE)$ FVC over time by treatment group
- The mean (± SE) FVC change from baseline by treatment group
- The LSmean (± SE) estimated FVC change from baseline over time by treatment group (as estimated in the primary analysis)

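### As written, the MMRM has no baseline-by-visit term, so the Week 48 difference can be biased if the baseline slope changes over time and dropout depends on baseline differently by arm (low priority, cheap to fix)

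*Protocol*

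**What the plan says.** Protocol 8.3.4.2 gives the fixed effects for QLF: "The MMRM model includes treatment, visit, treatment-visit interaction, randomization stratification factor, and baseline endpoint value as fixed effects". Protocol 8.3.4.3 carries this over to SGRQ, UCSD-SOBQ and LCQ, which "will be analyzed using same MMRM model as QLF".

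Protocol 8.3.4.1 planned a random coefficient model for FVC. SAP Section 7 replaces it with an MMRM as the primary FVC analysis. SAP 6.7.1.1.5 lists "fixed effects for treatment, visit (as a factor), treatment-by-visit interaction, randomization stratification factor, and covariates (baseline values, sex, age, race group, and height"). SAP 6.7.2.2.5 repeats the list for QLF and the other continuous endpoints, and drops sex, age, race group and height for FVCpp.

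In every list baseline is a main effect and treatment is the only term that interacts with visit. The covariance is unstructured first (SAP 6.7.1.1.6), and missing values in living subjects are assumed missing at random (SAP 6.7.1.1.3). SAP 6.7.1.1.5 points to example code in Appendix 7.1. That code is not visible in the text I worked from, so the written list is the only evidence of the model.

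**The concern.** The tested contrast is at Week 48. It is adjusted for baseline with a slope pooled over Weeks 6, 12, 18, 24, 36 and 48 for FVC, or Weeks 24 and 48 for QLF. With an unstructured covariance the pooled slope leans towards the visits with less variable change. If change becomes more variable over follow-up, those are the early visits. If the dependence of change on baseline also grows over time, the pooled slope is then too flat for Week 48.

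Under missing at random, the model's implied Week 48 values for living dropouts rest on the same slope. If the subjects still observed at Week 48 differ in baseline between arms, part of that difference is left in the treatment contrast. Roughly:

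bias ≈ (true Week 48 slope − pooled slope) × (between-arm difference in mean baseline among those observed at Week 48)

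Both factors must be non-zero. At stake are the primary FVC contrast and QLF, which is fourth in the fixed testing sequence (SAP Table 3).

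**Working it through.** **1. The plan's own figure.** Inputs from protocol 8.1: N = 340, power of 90% or more, two-sided alpha 0.05, a t-test on two samples, a 120 mL difference, a 300 mL SD in each arm, 1:1 allocation and about 20% dropout.

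- n per arm = 2 × (1.960 + 1.282)² × (300/120)² = 131.3, so 132 (133 with the exact t-test).
- Dropout: 132/0.8 = 165 per arm, 330 in total (334 from the t-test).
- With 340 × 0.8 / 2 = 136 completers per arm: SE = 300 × √(2/136) = 36.4 mL, 120/36.4 = 3.30, and power = Φ(3.30 − 1.96) = 91.0% (90.8% by t-test).

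So 340 reproduces. It rests on an unadjusted t-test and takes no credit for baseline adjustment, so the missing term does not alter it.

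**2. Simulation of the missing term.** The documents give no baseline slope, no correlation and no dropout pattern. All of these are assumed:

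- 340 subjects, 1:1, no true treatment effect, about 20% dropout.
- Maximum-likelihood MMRM with unstructured covariance, fitted with one common baseline slope and with one slope per visit.
- Baseline slope growing linearly over time. r is the correlation of baseline with Week 48 change.
- Residual variance growing over time. In the two-visit layout the Week 24 SD is 0.69 of the Week 48 SD and the two visits correlate at 0.61.
- Dropout either unrelated to baseline, or arm-opposite with a logit slope of +1 per baseline SD in one arm and −1 in the other. The second is a strong pattern.
- 800 runs per scenario with two visits (QLF layout), 250 with six (FVC layout).

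**3. Bias of the common-slope model under arm-opposite dropout.** Size only; the sign depends on which arm loses which subjects.

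| r | 2 visits: bias (SD), coverage | 6 visits: bias (SD), coverage | 6 visits × 300 mL |
|---|---|---|---|
| 0.1 | 0.02, 95% | 0.021, 96% | 6 mL |
| 0.3 | 0.06, 92% | 0.067, 91% | 20 mL |
| 0.5 | 0.09, 86% | 0.102, 84% | 31 mL |

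With visit-specific slopes the bias is at most about 0.01 SD, near Monte Carlo error, and coverage is 94-96%. In the two-visit layout the common-slope bias was near zero when the slope was constant over visits, and when dropout depended on baseline the same way in both arms.

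A milder pattern was also run for FVC. Only pamrevlumab dropout fell on the lower half of baseline, with assumed baseline SD 0.75 L, residual SD 0.30 L, and slope moving from about −0.02 to −0.09 or −0.12. The two models then differed by about 5 mL.

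**4. Width of the Week 48 interval, common slope divided by per-visit slopes.**

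| Dropout | Visits | r = 0.1 | r = 0.3 | r = 0.5 |
|---|---|---|---|---|
| Unrelated to baseline | 2 | 1.001 | 1.012 | 1.039 |
| Unrelated to baseline | 6 | 1.004 | 1.031 | 1.096 |
| Arm-opposite | 2 | 0.989 | 0.999 | 1.023 |
| Arm-opposite | 6 | 0.993 | 1.016 | 1.079 |

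With no baseline slope at any visit and dropout unrelated to baseline, the two-visit ratio is 1.000.

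**5. A source of changing slopes within the plan.** After death, values are set to the worst observed value (SAP 6.7.1.1.3 and 6.7.2.2.3). The imputed change is therefore a constant minus baseline, a slope of −1, and such records accumulate over visits. With an assumed 8.5% of deaths in each arm, the midpoint of the 6% and 11% reported for study 067 in protocol 2.6.3, this widened the interval by only about 0.1%.

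**The case against.** A main-effect baseline is a legitimate pre-specified choice. The documents establish neither a changing slope nor dropout that depends on baseline differently by arm, and the 20 mL figure comes from a deliberately strong dropout pattern. Protocol 2.6.3 does report that IPF progression was the most frequent cause of discontinuation in study 049, and that discontinuation of treatment for a serious event in study 067 was 6% against 13%. Those are small numbers and largely concern treatment rather than study exit. They make the pattern conceivable and no more. All of this stands, and it is why the point is a low-priority robustness step.

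The FVC sensitivity analyses also offer some protection. The jump-to-control and tipping-point imputations (SAP Appendices 7.2 and 7.3) regress each visit on baseline separately and then use a Week 48 ANCOVA, and the ranked ANCOVA uses Week 48 only. However, these change the missing-data handling at the same time, so a difference from the primary result could not be traced to one cause. The RCM sensitivity analysis lists no baseline-by-time term either. QLF and the questionnaires have no such analyses.

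A reader might infer that leaving the term out always widens the Week 48 interval. The figures do not support that. Widening needs slopes that vary by visit, is small for correlations up to 0.3, and reverses slightly at low correlation under arm-opposite dropout. A reader might also infer that the trial is underpowered. It is not on this ground, because the sample size calculation uses no baseline adjustment.

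Finally, the code in Appendix 7.1 may already contain the term. If so, the text and the code need to be reconciled.

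**Conclusion.** The written MMRM constrains the baseline slope to be equal at all visits, for the primary FVC analysis and for QLF, FVCpp and the questionnaires. This is an avoidable vulnerability rather than an error. The Week 48 difference is biased only if the slope changes over visits and dropout also depends on baseline differently by arm.

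Under strong arm-opposite dropout the FVC bias is about 6 mL (r = 0.1) to 20 mL (r = 0.3), or 5% to 17% of the 120 mL design difference (6/120 and 20/120). It is less under milder patterns. The correlation, the growth of the slope and the dropout pattern are all assumed, so the documents do not support the stronger statement that the planned estimate is biased.

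Precision is a secondary reason: interval width moves by about -1% to +3% for correlations up to 0.3, and not at all when the slope is constant and dropout is unrelated to baseline.

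**What to change.** Before unblinding:

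- Add baseline-by-visit interaction to the MMRM fixed effects in SAP 6.7.1.1.5 (FVC) and 6.7.2.2.5 (QLF, FVCpp, SGRQ, UCSD-SOBQ, LCQ), and report the Week 48 LSMean difference from that model.
- Align the model wording in protocol 8.3.4.2, or record the departure in SAP Section 7.
- Check the Appendix 7.1 code against the text and make them agree.

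The cost is one slope per extra visit: 1 degree of freedom for QLF (two visits) and 5 for FVC (six visits). No new data are needed. The one statistical downside is an interval about 1% wider when the slope varies little and dropout is unbalanced on baseline between arms.

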8.3.4.3. Exploratory Analyses

Patient reported outcomes (PROs) including SGRQ, UCSD-SOBQ and LCQ will be analyzed using same MMRM model as QLF. Absolute and relative FVCpp will be analyzed with similar RCM model as FVC excluding the covariates adjusted for FVCpp. Time to composite of respiratory hospitalization, absolute FVCpp decline $\geq 10\%$, or death will be analyzed similar to other secondary time-to-event endpoints. Biomarkers will be summarized.

8.3.5. Pharmacokinetic Analyses

A plan for population PK analysis will be provided in the population PK SAP.

8.3.6. Safety Analyses

Safety data will be summarized based on the Safety population. TEAEs and TESAEs will be summarized by treatment arm.

Clinically significant changes from baseline in vital signs and laboratory tests will be identified and summarized by treatment arm. Additionally, hypersensitivity/anaphylactic reactions will be monitored and immunogenicity reactions, including neutralizing HABA formation, will be assessed by the treatment arm.

8.4. Interim Analysis

No interim analysis is planned for this study.

8.5. Statistical Analysis Plan

The Statistical Analysis Plan (SAP) will include detailed analysis methods, statistical models, definitions, missing data handling as well as other data handling rules. It will document detailed analyses of the primary, secondary, and additional exploratory endpoints that are not otherwise specified in the protocol. The SAP will be finalized prior to database lock and treatment unblinding.

9. QUALITY CONTROL AND QUALITY ASSURANCE

9.1. Data Quality Assurance

Quality assurance and quality control systems will be implemented and maintained with Standard Operating Procedures by FibroGen and its designee(s), as appropriate, to ensure that this clinical study is conducted and data are generated, documented (recorded) and reported in compliance with the protocol, ICH E6 (GCP), and other applicable regulations.

This study will be monitored by FibroGen or designee in accordance with GCP, and may be audited or reviewed by an independent Quality Assurance department, IRB/IEC, and/or regulatory authorities. This implies that monitors and auditors/inspectors will have the right to inspect the study sites at any time during and/or after completion of the study and will have direct access to data/source documents, including the subject's file. By participating in this study, Investigators agree to this requirement.

The purpose of trial monitoring is to verify the following:

- The rights and well-being of human subjects are protected.
- The reported data are accurate, complete, and verifiable from source documents.
- All data are collected, tracked, and submitted by the site to FibroGen or designee, including unscheduled and missed assessments
- The reported data are reconciled across all data sources (e.g., laboratory, safety, IRT, clinical databases).
- The conduct of the trial is in compliance with the currently approved protocol/amendment(s), with GCP, and with the applicable regulatory requirement(s).

Measures will be undertaken to protect the confidentiality of records that could identify subjects, respecting the privacy and confidentiality rules in accordance with applicable regulatory requirements.

9.2. Audit and Inspection

Authorized representatives of the Sponsor, a regulatory authority, and/or an IRB/IEC may visit the Investigator site to perform audits or inspections, including source data verification and source documentation review. The Investigator will allow the Sponsor auditor (or designee), regulatory authority or ethics committee representative to inspect the drug storage area, study drug stocks, drug accountability records, subject charts (e.g. medical records) and study source documents, and other records relative to study conduct.

The purpose of an audit or inspection is to systematically and independently examine all study-related activities and documents to determine whether these activities were conducted, and data were recorded, analyzed, and accurately reported according to the protocol, ICH GCP guidelines, and any applicable regulatory requirements.

The Investigator must contact the Sponsor, or its third party representative (CRO), immediately if notified by a regulatory authority of an inspection pertaining to this study.

10. ETHICS

10.1. Ethical Considerations

The study will be conducted in accordance with applicable regulatory requirements, the International Conference on Harmonisation (ICH) E6 Guideline for Good Clinical Practice (GCP), the Declaration of Helsinki, any other applicable regulatory requirements, and Institutional Review Board (IRB) or Independent Ethics Committee (IEC) requirements.

10.2. Communication with the Institutional Review Board or Independent Ethics Committee

This protocol, the Informed Consent Form, the IB, and any information to be given to the subject must be submitted to a properly constituted IRB/IEC by the Investigator for review and approved by the IRB/IEC before the study is initiated and before any investigational product is shipped to the investigator. In addition, any subject recruitment materials must be approved by the IRB/IEC before the material is used for subject recruitment.

The Investigator is responsible for obtaining reapproval by the IRB/IEC annually or as required by the policies and procedures established by the IRB/IEC. Copies of the investigator's annual report and other required reports submitted to the IRB/IEC and copies of the IRB/IEC continuance of approval must be furnished to FibroGen or designee. A copy of the signed FDA Form 1572 or other qualified Investigator statement (as required) must also accompany the above approval letter provided to FibroGen.

Investigators are also responsible for promptly informing the IRB/IEC of any protocol changes or amendments, changes to the IB, and other safety-related communications from FibroGen or its designee. Written documentation of IRB/IEC approval must be received before the amendment is implemented.

Investigators must maintain a list of appropriate qualified persons to whom the Investigator has delegated significant trial-related duties and update the list as staff and their delegated responsibilities change.

10.3. Subject Information and Consent

Prior to participation in any study-specific procedures, the subject must sign an IRB/IEC-approved written Informed Consent Form (ICF) in his/her native language. The approved written informed consent must adhere to all applicable laws in regards to the safety and confidentiality of the subjects. To obtain and document informed consent, the Investigator should comply with applicable regulations, and adhere to ICH GCP standards and the ethical principles in the Declaration of Helsinki (2013, 64th, Fortaleza, Brazil).

The language in the written information about the study should be as non-technical as practical and should be understandable to the subject. Before informed consent is obtained, the Investigator should provide the subject ample time and opportunity to inquire about the study and to decide whether or not to participate.

All questions about the study should be answered to the satisfaction of the subject. The written ICF should be signed and personally dated by the subject and the person who conducted the

informed consent discussion, with any additional signatures obtained as required by applicable local regulations and IRB/IEC requirements. Each subject will be informed that participation is voluntary and that he/she can withdraw from the study at any time. All subjects will receive a copy of the signed and dated ICF.

If there are any changes to the IRB/IEC approved ICF during the subjects' participation in the study, the revised ICF must receive the IRB/IEC's written approval before use and subjects must be re-consented to the revised version of the ICF, if/as required by the IRB/IEC.

Each subject must provide his or her consent for the use and disclosure of personal health information in accordance with applicable regulatory requirements.

10.4. Subject Confidentiality

The confidentiality of records that could identify subjects should be protected, respecting the privacy and confidentiality rules in accordance with applicable regulatory requirements.

Subject medical information obtained as part of this study is confidential and may only be disclosed to third parties as permitted by the Informed Consent and HIPAA Authorization Form or separate authorization to use and disclose personal health information signed by the subject, or unless permitted or required by law.

11. DATA HANDLING AND RECORD KEEPING

11.1. Source Documents

Source documents are original documents, data, and records necessary for the reconstruction and evaluation of the clinical study. The Investigator or designee will prepare and maintain adequate and accurate source documents. These documents are designed to record all observations and other pertinent data for each subject enrolled in this clinical study. Source documents must be adequate to reconstruct all data transcribed onto the Case Report Forms (CRFs) and resolved queries.

11.2. Direct Access to Source Documents

The Investigator must provide direct access to source data and source documents for trial-related monitoring, audits, IRB/IEC review, and regulatory authority inspection. Direct access includes examining, analyzing, verifying, and reproducing any records and reports that are important to the evaluation of the study. The Investigator is obligated to inform and obtain the consent of the subject to permit such individuals to have access to his/her study-related records, including personal information and medical records.

11.3. Data Collection, Handling, and Verification

All required data will either be entered onto CRFs by authorized site personnel or will be provided as a data transfer from authorized service providers (such as laboratory results from a central laboratory). Data will be entered or uploaded into a validated, clinical database compliant with 21 CFR Part 11 regulations.

All subject data will be reviewed by Sponsor and/or designee. Data that appear inconsistent, incomplete or inaccurate will be queried for site clarification.

Medical history, adverse events and medications will be coded using industry standard dictionaries (e.g., MedDRA and World Health Organization Drug [WHODrug]) Dictionary.

The Investigator is responsible for reviewing, verifying, and approving all subject data (i.e. CRFs and queries) throughout the duration of the study and prior to study completion, ensuring that all data are verifiable with source documents.

